**Table 19 Guidelines for Management of Non-Hematologic Toxicities *During Induction* (cont.)**

Event		Action to Be Taken
New-onset neurologic manifestations suggestive of PML		
 
– Withhold study treatment.a
 
– Consult with a neurologist if PML is suspected (refer to Section 5.1.1.5 for guidance on investigations).
 
– If PML is ruled out, resume obinutuzumab or rituximab at full dose and resume polatuzumab vedotin and lenalidomide at current dose.
 
– If PML is confirmed, permanently discontinue study treatment.
 

AST, ALT, or bilirubin increase: Grade $\geq 3$ (or $\geq 10 \times$ ULN for patients with liver involvement)		
 
– Withhold study treatment and monitor liver enzymes at least every 7 days.
 
– Investigate etiology.
 
– If improvement to Grade <math>\leq 1</math>, resume obinutuzumab or rituximab and polatuzumab vedotin at full dose and resume lenalidomide at a reduced dosea per guidelines in Section 5.1.7.2 for current and subsequent cycles.
 
– Permanently discontinue study treatment for life-threatening liver toxicity.
 

Tumor flare reaction	Grade 3–4 c	
 
– Withhold study treatment.
 
– Administer corticosteroids, NSAIDs, and/or narcotic analgesics at investigator's discretion.
 
– If improvement to Grade <math>\leq 1</math>, resume obinutuzumab or rituximab and polatuzumab vedotin at full dose and resume lenalidomide at a reduced dosea per guidelines in Section 5.1.7.2 for current and subsequent cycles.
 

	Grade 1–2 c	
 
– Continue study treatment.
 
– Administer corticosteroids, NSAIDs, and/or narcotic analgesics at investigator's discretion.
 

**Table 19 Guidelines for Management of Non-Hematologic Toxicities *During Induction* (cont.)**

Event		Action to Be Taken
Neurotoxicity	Grade 4	– Permanently discontinue polatuzumab vedotin and all other study treatments.
	Grade 2 or 3	
 
– Withhold study treatment.a
 
– If improvement to Grade <math>\leq</math> 1 within 21 days, resume study treatments for current and subsequent cycles as follows (see guidelines in Section 5.1.7): 
 
– Resume obinutuzumab or rituximab at full dose.
 
– For patients who started at 1.8 mg/kg, resume polatuzumab vedotin at a reduced dose of 1.4 mg/kg per guidelines in Section 5.1.7.1; for patients who started at 1.4 mg/kg, permanently discontinue polatuzumab vedotin.a
 
– Resume lenalidomide at a reduced dosea per guidelines in Section 5.1.7.2.
 
 
 

Dermatologic toxicity: Grade $\geq$ 2	Grade 3 with blistering or Grade 4	– Permanently discontinue study treatment.
	Grade 2 or Grade 3 without blistering	
First occurrence:
 
 
– Withhold study treatment and evaluate patient at least every 7 days.
 
– Investigate etiology. Consult with a dermatologist.
 
– Topical or parenteral corticosteroids may be required.
 
– If improvement to Grade <math>\leq</math> 1, resume obinutuzumab or rituximab and polatuzumab vedotin at full dose and consider resuming lenalidomide at a reduced dosea per guidelines in Section 5.1.7.2 or continue current dose for current and subsequent cycles.
 
– Permanently discontinue all drugs in the event of angioedema, exfoliative or bullous rash, or if SJS or TEN is suspected.
 
 
Second occurrence:
 
 
– Permanently discontinue study treatment.
 

Venous thrombosis or embolism		
 
– Withhold lenalidomide.
 
– Start anticoagulation treatment.
 
– After patient has been stabilized on anticoagulants and any complications of the thromboembolic event have been managed, lenalidomide may be resumed at current dose at investigator’s discretion, dependent upon a benefit-risk assessment.
 
– Anticoagulants should be continued during the course of lenalidomide treatment.
 

**Table 19 Guidelines for Management of Non-Hematologic Toxicities During Induction (cont.)**

Event		Action to Be Taken
Other non-hematologic toxicities (i.e., not described above), excluding alopecia, nausea, and vomiting	Grade 3 or 4	
Grade 4 events
 
 
– Permanently discontinue study treatment.
 
 
Grade 3 events
 
 
– Withhold study treatment.
 
– If improvement to Grade <math>\leq 1</math> or baseline, resume obinutuzumab or rituximab at full dose and, if the event is considered related to lenalidomide, resume lenalidomide accordingly at a reduced dose as per guidelines in Section 5.1.7.2 for current and subsequent cycles.
 
– No more than two dose reductions of lenalidomide are allowed.
 

	Grade 2	
 
– Withhold study treatment.
 
– If improvement to Grade <math>\leq 1</math> or baseline, resume obinutuzumab or rituximab and polatuzumab vedotin at full dose and consider resuming lenalidomide at a reduced dosea per guidelines in Section 5.1.7.2 or continue current dose for current and subsequent cycles.
 

CT=computed tomography; DBLCL=diffuse large B-cell lymphoma; FL=follicular lymphoma; G-CSF=granulocyte colony-stimulating factor; IRR=infusion-related reaction; LMWH=low-molecular-weight heparin; NCI CTCAE=National Cancer Institute Common Terminology Criteria for Adverse Events; NSAID=nonsteroidal anti-inflammatory drug; PML=progressive multifocal leukoencephalopathy; SJS = Stevens-Johnson syndrome; TEN = toxic epidermal necrolysis; TLS=tumor lysis syndrome; ULN=upper limit of normal.

a Dose modifications apply only to events that are considered to be related to lenalidomide.

b According to Cairo-Bishop classification system.

c Graded according to NCI CTCAE, Version 3.0.

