#### **5.1.3.1 *Identified Risks***

On the basis of clinical experience with polatuzumab vedotin in patients treated in the current Phase I and II studies, neutropenia and peripheral neuropathy are identified risks of polatuzumab vedotin.

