#### **Peripheral Neuropathy**

Patients receiving polatuzumab vedotin may develop or experience worsening of peripheral neuropathy. Patients in clinical trials with polatuzumab vedotin should be monitored for symptoms of neuropathy (sensory and/or motor), including hypoesthesia, hyperesthesia, paresthesia, dysesthesia, discomfort, a burning sensation, weakness, gait disturbance, or neuropathic pain. Patients experiencing new or worsening peripheral neuropathy may require a dose delay, change in dose, or discontinuation of treatment and should be managed according to the protocol. Study treatment dose and schedule modifications for peripheral neuropathy are described in Section 5.1.7.3.

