### **5.1.5 Risk of Overlapping Toxicities**

The anticipated toxicities from the combined administration of obinutuzumab *or* rituximab with polatuzumab vedotin and lenalidomide are expected to be manageable in the clinical setting and will be closely monitored throughout the study.

Rituximab was safely combined with polatuzumab vedotin in patients with R/R FL or DLBCL. Grade 3 or 4 neutropenia (21%) appeared to be the most important hematologic adverse event associated with this combination. When given as monotherapy for the treatment of patients with R/R B-cell lymphoma, obinutuzumab was associated with 5% Grade 3 or 4 neutropenia. Because obinutuzumab is expected to have an incidence of neutropenia that is higher than that with rituximab monotherapy, there is a risk of increased incidence of neutropenia. Obinutuzumab and polatuzumab vedotin for the treatment of patients with R/R FL or DLBCL is currently being assessed in Study GO27834. As these new data emerge, they will be assessed and applied to update this study if required.

Lenalidomide has also been associated with hematologic adverse events, including neutropenia. When lenalidomide was combined with obinutuzumab, the incidence of Grade 3 or 4 neutropenia was reported to be 33.3% ([Morschhauser et al. 2014b](#)). Therefore, the combination of G+Pola+Len is anticipated to result in overlapping hematologic toxicity, for which patients will be closely monitored. Guidelines for the management of patients who develop hematologic toxicities are provided in Sections [5.1.7.3](#) and [5.1.7.4](#). In addition to the standard hematologic monitoring, patients enrolled in this study will be closely monitored for evidence of infections.

Because both polatuzumab vedotin and lenalidomide have been associated with a risk of peripheral sensory neuropathy, it is unknown whether this risk may be increased when they are combined. Therefore, peripheral neuropathy will be closely monitored, and guidelines for management for patients who develop neurotoxicity (i.e., peripheral neuropathy, sensory and/or motor) are provided in Sections 5.1.3.1 and 5.1.4.10, and in Table 19.

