### 5.1.7 Management of Specific Adverse Events

Study treatment may be delayed for toxicity for a maximum amount of time, as specified in [Table 17](#), [Table 18](#), and [Table 19](#). If study treatment is delayed for longer than the specified maximum amount of time, study treatment will be permanently discontinued. When a treatment cycle is delayed because of toxicity resulting from any component of the regimen, all study treatment should be held and resumed together to remain synchronized. If one drug is discontinued, treatment with the other two drugs may be continued for patients experiencing clinical benefit as determined by the investigator after discussing with the Medical Monitor.

Treatment delays apply to all toxicities described below; dose modifications apply only to toxicities that are considered to be related to lenalidomide or polatuzumab vedotin (only for peripheral neuropathy). There will be no dose reductions of obinutuzumab or *rituximab*. *For patients receiving obinutuzumab, if toxicity occurs before Cycle 1 Day 8 or Cycle 1 Day 15, these doses of obinutuzumab will not be skipped but given after resolution of toxicity.*

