#### 5.1.7.1 Polatuzumab Vedotin Dose-Reduction Steps

The dose of polatuzumab vedotin may be reduced *due to neurotoxicity only* according to the following dose reduction steps based on the starting dose (see [Table 15](#) and [Table 19](#)).

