### 5.3.4 Assessment of Causality of Adverse Events

Investigators should use their knowledge of the patient, the circumstances surrounding the event, and an evaluation of any potential alternative causes to determine whether or not an adverse event is considered to be related to any of the study treatment

components, indicating "yes" or "no" accordingly. The following guidance should be taken into consideration:

- Temporal relationship of event onset to the initiation of study treatment
- Course of the event, considering especially the effects of study treatment modifications or discontinuation, or reintroduction of study treatment (as applicable)
- Known association of the event with the study treatment or with similar treatments
- Known association of the event with the disease under study
- Presence of risk factors in the patient or use of concomitant medications known to increase the occurrence of the event
- Presence of non-treatment-related factors that are known to be associated with the occurrence of the event

For patients receiving combination therapy, causality will be assessed individually for each protocol-mandated therapy.

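### Table 19 footnote a limits dose changes to lenalidomide-related events and, read literally, cancels the polatuzumab reduction for neuropathy attributed to polatuzumab alone

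*Combined protocol and SAP*

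**What the plan says.** Table 19 (Section 5.1.7.3) gives the induction rules for non-hematologic toxicity. For Grade 2 or 3 neurotoxicity that recovers to Grade 1 or better within 21 days, the polatuzumab bullet has two parts. Patients who started at 1.8 mg/kg "resume polatuzumab vedotin at a reduced dose of 1.4 mg/kg per guidelines in Section 5.1.7.1". Patients who started at 1.4 mg/kg stop the drug. The bullet closes with marker a, and footnote a states: "Dose modifications apply only to events that are considered to be related to lenalidomide".

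The surrounding sections set a different scope:

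- Section 5.1.7: "dose modifications apply only to toxicities that are considered to be related to lenalidomide or polatuzumab vedotin (only for peripheral neuropathy"; the parenthesis closes there.
- Section 5.1.7.1 permits a polatuzumab reduction for neurotoxicity only, "according to the following dose reduction steps based on the starting dose". Table 15 gives the single step, 1.8 to 1.4 mg/kg. Neither mentions relatedness to lenalidomide.
- Section 5.3.4: for combination therapy, "causality will be assessed individually for each protocol-mandated therapy".
- Section 5.1.3.1: "neutropenia and peripheral neuropathy are identified risks of polatuzumab vedotin".

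**The concern.** The footnote makes a polatuzumab dose step depend on whether the event is related to a different drug. An investigator who attributes neuropathy to polatuzumab and not to lenalidomide is told by the row to reduce polatuzumab, and by the footnote on the same bullet that dose modifications do not apply.

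This is the only row of Table 19 that reduces polatuzumab, and other sections send sites to it. Section 5.1.3.1 says: "Study treatment dose and schedule modifications for peripheral neuropathy are described in Section 5.1.7.3". Section 5.1.5 and Section 5.1.7.1 also refer to Table 19. At stake is whether a patient recovering from a known polatuzumab toxicity is re-exposed at the full dose or at the reduced one, and whether all sites answer that question in the same way.

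**Working it through.** The plan states no figure to reproduce here. The check is a comparison of rules, followed by a short dose calculation.

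**Test case.** A patient starts polatuzumab at 1.8 mg/kg and develops Grade 2 or 3 neuropathy, which recovers to Grade 1 or better within 21 days. It is judged related to polatuzumab and not to lenalidomide, and induction cycles remain.

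| Source | Condition on the polatuzumab reduction | Result for the test case |
|---|---|---|
| Table 19, row text | None on relatedness | Restart at 1.4 mg/kg |
| Section 5.1.7 | Related to lenalidomide or, for peripheral neuropathy, to polatuzumab | Reduction is within scope |
| Section 5.1.7.1 and Table 15 | Neurotoxicity only | Reduction to 1.4 mg/kg is permitted |
| Table 19, footnote a | Related to lenalidomide | No dose modification |

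The first three agree and the footnote contradicts them.

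**Can the case arise?** Yes. Section 5.3.4 requires a separate causality judgement for each drug, and Section 5.1.3.1 lists neuropathy as an identified polatuzumab risk. Section 5.1.4.10 reports no increase in neuropathy with long-term lenalidomide in newly diagnosed myeloma, so attribution to polatuzumab alone is a reasonable call.

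**Where there is no conflict.**

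- Events attributed to both drugs satisfy the footnote. Section 5.1.5 allows for this, since "both polatuzumab vedotin and lenalidomide have been associated with a risk of peripheral sensory neuropathy".
- Withholding treatment, the stop after more than 21 days and the Grade 4 stop do not depend on the footnote.
- Discontinuation in 1.4 mg/kg starters would be caught only if stopping counts as a dose modification. The protocol lists the two separately (for example in Sections 4.3.2.3, 5.1 and 5.3.5.5), so that part is not claimed.

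**Dose difference.** Inputs are 1.8 and 1.4 mg/kg (Tables 15 and 19) and six induction cycles (Section 4.3.2). The footnote names no alternative dose, so a restart at 1.8 mg/kg is an inference from its literal reading.

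- Difference per remaining cycle: 1.8 − 1.4 = 0.4 mg/kg
- Relative to the dose: 0.4 / 1.8 = 22.2%
- Planned induction total: 6 × 1.8 = 10.8 mg/kg
- Share of the total per remaining cycle: 0.4 / 10.8 = 3.7%
- Upper limit, if the event follows the first dose and five remain: 5 × 0.4 = 2.0 mg/kg, and 2.0 / 10.8 = 18.5%
- Lower limit, if the event follows the last polatuzumab dose: zero

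**The case against.** The strongest reply is that the correct instruction is in the same bullet. The row names the drug and the dose and cites both sections, and Section 5.1.7, Section 5.1.7.1 and Table 15 are consistent with it. A site would have to let a general note override a specific order. Where Table 19 wants polatuzumab left unchanged, as in the PML row, it says so. This stands: the intended rule can be recovered, and it limits the consequence.

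A second point concerns placement. The marker follows the discontinuation clause, whereas elsewhere in the table it often comes directly after the words on reduced lenalidomide dosing. It also sits on lines that only withhold treatment, where it cannot restrict anything because Section 5.1.7 applies delays to all toxicities. So the marker is used loosely. But a marker at the end of a bullet is fairly read as covering the whole bullet, and the footnote speaks of dose modifications, which describes the reduction better than the discontinuation.

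A third point is that Section 5.1.7.1 is permissive and Section 5.1.7 only sets scope, so the row alone makes the reduction mandatory. That is correct. It does not remove the contradiction, because the footnote is attached to that row.

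Finally, the affected case needs several conditions to coincide, and no patient count can be given. That is accepted.

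**Conclusion.** The concern holds. Footnote a, as attached to the polatuzumab bullet, contradicts the row text and Section 5.1.7, and sets a condition absent from Section 5.1.7.1. Followed literally, it is a wrong safety dosing rule for one defined case: neuropathy attributed to polatuzumab alone, in a 1.8 mg/kg starter who recovers in time with cycles remaining. Those at risk are DLBCL patients, whose dose is fixed at 1.8 mg/kg (Section 4.3.2.3), and FL patients who start at that dose.

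The size is 0.4 mg/kg per remaining cycle for each affected patient. This assumes that the marker covers the whole bullet and that no modification means restarting at 1.8 mg/kg. The number of affected patients cannot be derived from the documents. The study's neuropathy and dose-intensity results remain interpretable. The point should be fixed because the text governs dosing after a known toxicity and is easily corrected, not because it threatens the trial's conclusions.

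**What to change.** On the polatuzumab bullet of the Grade 2 or 3 neurotoxicity row, either remove marker a or replace it with a new footnote stating the Section 5.1.7 rule: dose modifications apply to toxicities related to lenalidomide or, for peripheral neuropathy only, to polatuzumab. The new footnote is the better choice, because it puts the rule where sites read it while marker a remains on the withholding line of the same row. Keep footnote a on the lenalidomide steps, where it is correct.

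The cost is one footnote marker, or one added footnote, in an amendment. It adds no procedures, visits or patients.

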#### 5.1.7.4 Toxicities during Consolidation or Maintenance Treatment

Table 20 provides guidelines for management of toxicities that occur during consolidation or maintenance treatment.

**Table 20 Guidelines for Management of Toxicities that Occur during Consolidation or Maintenance Treatment**

Event	Action to Be Taken
Hematologic toxicity: Grade 3 or 4	

– Withhold obinutuzumab or rituximab and lenalidomide.

– Administer G-CSF for neutropenia per institutional guidelines.

– Administer RBCs or platelets as required.

– If improvement to Grade <math>\leq 2</math>, resume obinutuzumab or rituximab and lenalidomide at same dose. Lenalidomide dose may be reduced by one dose level per investigator judgment following discussion with the medical monitor.

– If study treatment is withheld for <math>> 42</math> days, permanently discontinue study treatment.

Non-hematologic toxicity: Grade $\geq 2$	

– Withhold obinutuzumab or rituximab and lenalidomide.

– If improvement to Grade <math>\leq 1</math> or baseline, administer study treatment at full dose. Lenalidomide dose may be reduced by one dose level per investigator judgment following discussion with the medical monitor.

– If study treatment is withheld for <math>> 42</math> days, permanently discontinue study treatment.

G-CSF=granulocyte colony-stimulating factor.

## 5.2 SAFETY PARAMETERS AND DEFINITIONS

Safety assessments will consist of monitoring and recording adverse events, including serious adverse events and non-serious adverse events of special interest, performing protocol-specified safety laboratory assessments, measuring protocol-specified vital signs, and conducting other protocol-specified tests that are deemed critical to the safety evaluation of the study.

Certain types of events require immediate reporting to the Sponsor, as outlined in Section 5.4.

### 5.2.1 Adverse Events

According to the ICH guideline for GCP, an adverse event is any untoward medical occurrence in a clinical investigation subject administered a pharmaceutical product, regardless of causal attribution. An adverse event can therefore be any of the following:

- Any unfavorable and unintended sign (including an abnormal laboratory finding), symptom, or disease temporally associated with the use of a medicinal product, whether or not considered related to the medicinal product

- Any new disease or exacerbation of an existing disease (a worsening in the character, frequency, or severity of a known condition), except as described in Section [5.3.5.10](#)
- Recurrence of an intermittent medical condition (e.g., headache) not present at baseline
- Any deterioration in a laboratory value or other clinical test (e.g., ECG, X-ray) that is associated with symptoms or leads to a change in study treatment or concomitant treatment or discontinuation from study treatment.
- Adverse events that are related to a protocol-mandated intervention, including those that occur prior to assignment of study treatment (e.g., screening invasive procedures such as biopsies)

### **5.2.2 Serious Adverse Events (Immediately Reportable to the Sponsor)**

A serious adverse event is any adverse event that meets any of the following criteria:

- Is fatal (i.e., the adverse event actually causes or leads to death)
- Is life threatening (i.e., the adverse event, in the view of the investigator, places the patient at immediate risk of death)
  - This does not include any adverse event that had it occurred in a more severe form or was allowed to continue might have caused death.
- Requires or prolongs inpatient hospitalization (see Section [5.3.5.11](#))
- Results in persistent or significant disability/incapacity (i.e., the adverse event results in substantial disruption of the patient's ability to conduct normal life functions)
- Is a congenital anomaly/birth defect in a neonate/infant born to a mother exposed to study treatment
- Is a significant medical event in the investigator's judgment (e.g., may jeopardize the patient or may require medical/surgical intervention to prevent one of the outcomes listed above)

The terms "severe" and "serious" are not synonymous. Severity refers to the intensity of an adverse event (e.g., rated as mild, moderate, or severe, or according to NCI CTCAE criteria; see Section [5.3.3](#)); the event itself may be of relatively minor medical significance (such as severe headache without any further findings).

Severity and seriousness need to be independently assessed for each adverse event recorded on the eCRF.

Serious adverse events are required to be reported by the investigator to the Sponsor immediately (i.e., no more than 24 hours after learning of the event; see Section [5.4.2](#) for reporting instructions).

### **5.2.3 Adverse Events of Special Interest (Immediately Reportable to the Sponsor)**

Adverse events of special interest are required to be reported by the investigator to the Sponsor immediately (i.e., no more than 24 hours after learning of the event; see Section 5.4.2 for reporting instructions). Adverse events of special interest for this study include the following:

- Cases of potential drug-induced liver injury that include an elevated ALT or AST in combination with either an elevated bilirubin or clinical jaundice, as defined by Hy's law (see Section 5.3.5.7)
- Suspected transmission of an infectious agent by the study treatment, as defined below:

Any organism, virus, or infectious particle (e.g., prion protein transmitting transmissible spongiform encephalopathy), pathogenic or non-pathogenic, is considered an infectious agent. A transmission of an infectious agent may be suspected from clinical symptoms or laboratory findings that indicate an infection in a patient exposed to a medicinal product. This term applies only when a contamination of any of the study treatment components is suspected.
- TLS of any grade, irrespective of causality
- *Second malignancies*

